## ANALYSIS STATISTICAL

A descriptive analysis of the data will be carried out. The qualitative variables will be presented with their absolute frequency and percentage. Gaussian quantitative variables will be presented with their mean and standard deviation (SD) and non-Gaussian variables as median [minimum-maximum]. For the comparison of two qualitative variables, the McNemar and Chi-square tests will be used; For the comparison of quantitative variables, and due to the small sample size, the non-parametric Mann-Whitney U, Kruskal-Wallis, Wilcoxon and Friedman tests will be used. Subsequently, a regression analysis will be carried out using Mixed Models (since although the sample size is very small, mixed models allow the data to be analyzed, correcting this problem with multiple measurements per individual). The accepted  $\alpha$  risk for all hypothesis tests will be 0.05. The data will be analyzed with the SPSS 15.0 statistical package and the free R software.

For the analysis of EEG data, a Power will be used. Spectrum Analysis (PSA) with the EEGLAB toolbox or similar. This technique will allow us to evaluate the energy distribution in different frequency bands of brain signals. EEG signals are decomposed into their frequency components using mathematical transforms, such as the Fourier transform, and the power in each specific frequency band is calculated.

PSA focuses on the decomposition of EEG signals into different frequencies. This will allow us to understand the distribution of energy in the frequency domain. Some of the main variables that can be analyzed are:

- Frecuencias: aquí se analizarán diferentes bandas de frecuencia, donde por las características del EMOTIV se pueden incluir algunas como:
  - Theta (4-8 Hz)
  - Alfa (8-13 Hz)
  - Low Beta (12-16 Hz)
  - High Beta (16-25 Hz)
  - Gamma (25-45 Hz)

Each of these bands is related to specific mental states and cognitive functions. For example, the delta band (0.5-4 Hz) is associated with deep sleep, while the alpha band (8-13 Hz) is associated with states of relaxation or non-stressful alertness.

PSA will allow quantification of electrical activity in these bands, which provides crucial information for understanding brain activity.

- Amplitudes: we will be able to quantify the amplitude of the waves in each frequency band. This involves measuring the magnitude of EEG signals in each specific frequency range.

In general, these variables provide critical information about the brain's electrical activity. This will allow us to assess associated neurological disorders and the study of the patient's cognition

Therefore, this technique will allow us to identify abnormal patterns of brain activity, evaluate brain responses during resting-state EEG data acquisition, and examine the relationship between activity in different frequency bands and specific cognitive functions. and will allow us to deepen our understanding of brain electrical activity and its correlation with cognitive processes and mental states.

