## **HYPOTHESIS AND OBJECTIVES**

### **1. Hypothesis**

According to the evidence from the literature, it is proposed that participation in a therapeutic dance therapy program will have a significant positive effect on the scores of neurocognitive tests and on the electroencephalographic activity patterns of patients diagnosed with severe mental disorder (SMD). Specifically, it is expected that after the intervention, participants will show significant improvements in memory and executive functions compared to the control group without intervention.

From a more theoretical perspective, our null and alternative hypotheses are:

- Null Hypothesis (H0): there is no significant difference between the neurocognitive test scores and the electroencephalographic activity patterns of people with SMD who participate in a dance therapy therapeutic program and those who do not.
- Alternative Hypothesis (H1): Participation in a therapeutic dance therapy program will have a significant positive effect on neurocognitive test scores and electroencephalographic activity patterns of people diagnosed with SMD.

Specifically, it is expected that after the intervention:

- H1a: People participating in the dance therapy program show significant improvements in memory test scores compared to the control group.
- H1b: People participating in the dance therapy program show significant improvements in executive functions compared to the control group.

Our hypothesis is based on a solid theoretical foundation, which suggests that dance therapy could promote neuroplasticity and improve cognition through body movement. To this end, we will conduct this carefully controlled study, collecting pre and post intervention data in both groups and using appropriate statistical analyses.

To test this hypothesis, a controlled study will be carried out with an experimental group participating in the dance therapy program and a control group that will not. Neuropsychological test scores and electroencephalography data will be compared before and after the intervention to assess any significant changes in cognitive function and brain activity.

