**e. Sample size calculation.**

The present study aims to determine the number of participants needed to determine the effect of a dance therapy program administered to patients with severe mental disorders. Preliminary studies cited in the literature have determined that dance therapy has the potential to influence aspects such as emotional state, memory or executive functions, being observable through neuropsychological and EEG tests. The working hypothesis is that dance therapy will produce a statistical effect, involving cognitive improvement, observable in subsequent assessments of neuropsychological test scores and electroencephalographic activity patterns in those diagnosed with severe mental disorder. Therefore, in this study we tried to determine two independent sample means.

The calculation of statistical power was performed by means of two independent ("unilateral") means, based on the variance of a control group and the reference group with a minimum of 13 study subjects, in accordance with systematic reviews of previous scientific studies such as Jiménez et al. (2019). The probability of the degree of statistical significance was based on values of  $p<0.05$  with the statistical tests applied, with a 95% confidence interval.

The sample was calculated using GRANMO software (Marrugat et al., 1998). In this line, in order to estimate the probability that the observed phenomenon is true and not due to chance with the calculated sample size, the alpha risk was determined. Specifically, an  $\alpha=0.05$  was chosen, which assumes a 95% confidence level. To control for the potential of the analysis, a power of 80% was selected, with a beta of 0.2. To define the ratio between two groups (control and experimental), the ratio between group 1 and group 2 was indicated, the ratio being a value of 1, as these are two groups with equal sample sizes. In addition, as we are calculating on the basis of means, the standard deviation has been included. Since we do not have a pilot project with previous data before and after the dance therapy program proposed in the current project, the following process was used to find the standard deviation:

1. Review of previous literature on mental health and dance therapy; 2. Screening of dance therapy manuscripts with patients presenting with a pathology encompassed

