intervention program with dance therapy with the experimental group. In particular, to find the standard deviation of our control group sample with severe mental disorder, the mean values of the negative symptoms of the PANSS scale were chosen again (as they show significant statistical differences in scores between the control group and the experimental group in the manuscript of Chao & Xiaolin, 2022). In this case, the control group presented a mean of 14.98 on negative symptoms before the parallel start of the dance therapy intervention program, and a mean of 11.32 after the conclusion of the dance therapy intervention stage in the experimental group. Considering these means, we proceeded to calculate the sample standard deviation with the same procedure and software previously used to find the standard deviation of the intervention group in the previous point. Here we obtained a value for the sample standard deviation of our control group of 2.588.

In addition to the above, as the starting hypothesis is that the dance therapy program will improve emotional management and increase cognitive performance, it can be assumed that the minimum response to the program will be double (2).

After performing the mathematical calculation, accepting an alpha risk of 0.05 and a beta risk of 0.2 in a unilateral contrast, 28 participants in the intervention group are required to detect a difference equal to or greater than 2,822 units, as well as 28 participants in the control group to detect a difference equal to or greater than 2,588 units.

In addition, an expected rate or proportion of loss to follow-up of 10% ( $10/100=0.1$ ) due to experimental errors, drop-out, etc., has been estimated in the intervention group, with participants engaged in the dance therapy intervention. On the other hand, a loss-to-follow-up rate or proportion of 25% ( $25/100=0.25$ ) has been estimated in the control group with participants not engaged in the dance therapy intervention. This expected increase in losses in the control group is based on the hypothesis that the patient who does not receive the intervention may not be as involved in the experiment or, eventually, debut with pathological manifestations associated with their medical condition leading to absenteeism or indisposition during the data collection stage.

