## **PROCEDURE or DESCRIPTION OF THE STUDY**

### **1. Workplan**

All the tests (BASC, MoCA, PANSS and EEG) will be carried out with the 47 patients with SMD to find out their baseline status. The people with SMD will be randomly assigned to an experimental group (dance therapy program) or a control group (without intervention in dance therapy but with regular pharmacological treatment). The study will last approximately 1 year between the administration of tests, the program and the analysis of results. The dance therapy program will last 20 sessions over 10 weeks. The sessions will take place at the headquarters of the Asociación Canaria de Terapias Creativas (ASCATEC) in the Siglo XXI space in Santa Cruz de Tenerife.

The 26 people with SMD in the experimental group will participate in a 10-week intervention program with 2 sessions per week in which they will work for 1 hour on memory, attention and executive functions through dance and movement, ending with 10 minutes of Mindfulness.

The 21 people in the control group will not receive any type of dance therapy intervention, but will continue with their usual pharmacological treatment.

The effects will be measured after a treatment of 20 sessions (twice a week). Results will be obtained by analyzing EEG parameters (EEG amplitude and frequency) and cognitive functions (BACS and MoCA). On the other hand, at the end of the 20-session program, tests will also be administered to assess the symptomatology of the severe mental disorder suffered by the person (PANSS) to assess the effects of the program on these variables.

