### **3. Data Collection**

The tests will be administered after randomization and before starting the intervention to measure the basal state of each participant and after the completion of the dance therapy program in order to determine the changes generated with the dance therapy program. The tests will also be repeated after 3 months as a follow-up of the results obtained.

All registrations will be done anonymously, assigning each person an identification number. All data will be kept for 5 years.

- **Brief assessment of cognition in schizophrenia (BACS)** (Keefe et al., 2004): serves to quantify cognitive impairment in schizophrenia and/or psychosis. The BACS includes assessments of verbal memory, working memory (Digit Stream), motor speed (Token Motor), verbal fluency, attention and processing speed (Symbol

Coding), and executive function (Tower of London). The minimum and maximum scores on the BACS for each subtest are:

1. Token Motor Task (TMT): The minimum score is 0, and the maximum is 100.
2. List Learning: The minimum score is 0, and the maximum is 50.
3. Digital Sequencing Task: The minimum score is 0, and the maximum is 21.
4. Semantic Fluency: The minimum score is 0, and the maximum is 40.
5. Symbol Coding: The minimum score is 0, and the maximum is 50.
6. Tower of London: The minimum score is 0, and the maximum is 21.
7. Verbal Memory: The minimum score is 0, and the maximum is 20.

These scores are used to evaluate performance on each of the BACS subtests.

Subsequently, it is common to calculate a composite score that summarizes the individual's overall cognitive performance. For the interpretation of results, see the **attached technical sheet**. In our case, all patients in the intervention group will be patients with a diagnosis of psychosis without comorbidities.

- **Montreal Cognitive Assessment (MoCA)** (Ramírez et al., 2014): it is a 30-question test that evaluates mild cognitive dysfunctions by assessing executive function and visuospatial ability, identification, short-term memory, delayed recovery, attention, language, abstraction, animal naming and orientation. The ratings range from 0 to 30 and the cut-off value to determine a normal score is >26 points. The test is administered in about 10-12 minutes.

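### No baseline-adjusted between-arm analysis is secured: the rank tests take no covariate, and the mixed model that follows does not say how baseline enters

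*Combined protocol and SAP*

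**What the plan says.** - **Tests named.** Analysis Statistical, on quantitative variables: "and due to the small sample size, the non-parametric Mann-Whitney U, Kruskal-Wallis, Wilcoxon and Friedman tests will be used".
- **Model named next.** The same paragraph continues: "Subsequently, a regression analysis will be carried out using Mixed Models". The reason given is that "mixed models allow the data to be analyzed, correcting this problem with multiple measurements per individual". Outcome, fixed effects, any arm-by-visit term, the role of the baseline score and the status of the model relative to the rank tests are not given.
- **Baseline data.** Procedure, 1. Workplan (where BACS is spelled BASC): "BASC, MoCA, PANSS and EEG) will be carried out with the 47 patients with SMD to find out their baseline status". Section 3, Data Collection, places these tests before the intervention and again at its end, and adds: "The tests will also be repeated after 3 months as a follow-up of the results obtained".
- **What is to be compared.** H1a and H1b are claims of improvement relative to the control group, and the Hypothesis section promises "collecting pre and post intervention data in both groups and using appropriate statistical analyses". Secondary objective 1 compares scores between groups; objectives 2 and 3 refer to changes.
- **Sample size basis.** Section 2e: "in this study we tried to determine two independent sample means", and "accepting an alpha risk of 0.05 and a beta risk of 0.2 in a unilateral contrast, 28 participants in the intervention group are required".

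**The concern.** The hypotheses are about differences between arms, and every outcome has a pre-programme measurement. In a trial of 47 patients the baseline score of the same test is usually the strongest predictor available, and adjusting for it reduces the residual variance at no cost in data. The tests listed first cannot do this. The model listed second could, but nothing says that it will.

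Two things are at stake. The first is precision: depending on how the analyst fills the gap, power can differ by tens of percentage points. The second is conditional bias: with 26 and 21 patients a noticeable chance difference at baseline is common, and the candidate analyses treat it differently. Since no analysis is named as primary, the choice among post-score ranks, change-score ranks and various mixed models could be made after the data are seen.

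The stated reason for rank tests is small size. Small size is also where recovering precision from baseline is most useful, and 47 patients are enough to fit one covariate.

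**Working it through.** **1. The plan's own figure.** With difference 2, one-sided 0.05 and 80% power, n per arm = 2 × [SD × (1.645 + 0.842) / 2]².
- SD 2.822: 24.62, so 25; 25 / 0.90 = 27.8, so 28.
- SD 2.588: 20.70, so 21; 21 / 0.75 = 28.

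The stated 28 per arm is reproduced, with 2 units as the difference and dropout already included. I therefore use 2 units and the average SD, (2.822 + 2.588) / 2 = 2.705, which is 2 / 2.705 = 0.74 SD.

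**2. Variance under each analysis**, relative to unadjusted post scores. Rho, the baseline-outcome correlation, is assumed.
- Baseline-adjusted model: 1 − rho².
- Change score: 2(1 − rho). With complete data at two visits, a mixed model with baseline as a further outcome and free arm means gives this same contrast.
- Ratio of the first to the second: (1 + rho) / 2, which is below 1 for every rho below 1.

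| rho | 0.3 | 0.5 | 0.7 | 0.8 |
|---|---|---|---|---|
| Adjusted, 1 − rho² | 0.91 | 0.75 | 0.51 | 0.36 |
| Change, 2(1 − rho) | 1.40 | 1.00 | 0.60 | 0.40 |

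**3. One power calculation in full** (26 and 21, rho 0.5, two-sided). √(1/26 + 1/21) = 0.293.
- Adjusted: SE = 2.705 × √0.75 × 0.293 = 0.687; 2 / 0.687 − 1.96 = 0.95; power 83%.
- Change: SE = 2.705 × 1.00 × 0.293 = 0.794; 2 / 0.794 − 1.96 = 0.56; power 71%.

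This normal approximation is slightly optimistic at this size. Simulation with normal data gives 81% and 68%.

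**4. Simulated power, 26 and 21 patients.** A repeat with 6,000 trials per setting agreed within 2 points.

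| Analysis | Sides | 0.3 | 0.5 | 0.7 | 0.8 |
|---|---|---|---|---|---|
| Baseline-adjusted model | 2 | 71% | 81% | 92% | 98% |
| Change-score t-test | 2 | 55% | 68% | 89% | 97% |
| Mann-Whitney on change | 2 | 52% | 65% | 87% | 97% |
| Mann-Whitney on post scores | 2 | 66% | 66% | 66% | 66% |
| Baseline-adjusted model | 1 | 81% | 89% | 96% | 99% |
| Change-score t-test | 1 | 67% | 80% | 95% | 99% |
| Mann-Whitney on post scores | 1 | 77% | 77% | 77% | 77% |

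Two-sided gain of the adjusted model at rho 0.3/0.5/0.7/0.8:
- over the change-score t-test: 16, 13, 3 and 1 points;
- over Mann-Whitney on change: 19, 16, 5 and 1 points;
- over Mann-Whitney on post scores: 5, 15, 26 and 32 points.

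With no true difference, simulated type I error stayed near 0.05 for every method.

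**5. Chance imbalance.** The SD of the baseline difference is 0.293 SD units, so a gap above 0.3 SD has probability 2 × [1 − Φ(0.3 / 0.293)] = 0.31. A post-only comparison is shifted by rho × gap: for a gap of 0.3 SD, 0.15 SD at rho 0.5 and 0.24 SD at rho 0.8. A change-score contrast over-corrects by (1 − rho) × gap: 0.15 SD and 0.06 SD.

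**The case against.** The best defence is that the plan does not stop at rank tests. The very next sentence brings in mixed models, and their form is open: baseline as a covariate, or a common baseline mean for the two arms, is as compatible with the text as any weaker form. Objectives 2 and 3 speak of changes, so comparison on post scores alone is not what the documents clearly intend. Against a change-score contrast the gain is small once rho reaches 0.7, and smaller still one-sided, which is how the sample size was set: 14, 9, 1 and 0 points at rho 0.3/0.5/0.7/0.8.

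Much of this stands, and it rules out stronger readings. A reader might infer that the plan discards the baseline information or leaves imbalance uncorrected. The text does not support that: the mixed model could be specified well, and even its unconstrained form subtracts the baseline gap. A reader might also infer that this is the costliest analysis choice in the plan; no other choice has been sized against it.

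What the defence does not supply is a commitment. The only reason given for the mixed model is repeated measurement per patient, which says nothing about baseline, and no analysis is named as primary.

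**Conclusion.** The point holds as a gap with a concrete better method available: no baseline-adjusted comparison of arms is secured, although every outcome has a baseline score. The adjusted model was at least as powerful as every alternative at each rho examined. Its advantage is large over post-score ranking when rho is 0.5 or more. Over change-based analyses it is material at 0.3 to 0.5 and minor at 0.7 to 0.8.

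The conclusion rests on these assumptions:
- Rho is not in the documents; 0.3 to 0.8 is an assumed range and may differ between the cognitive tests, PANSS and EEG.
- The SDs of 2.822 and 2.588 are SDs of published PANSS negative-symptom group means, not of patients or of a cognitive score. Absolute powers are therefore illustrative; the variance ratio 1 − rho² does not depend on them.
- 26 and 21 are taken as the numbers analysed, as in section 2e. The Design and Workplan sections also use 47 as the number entering. On that one reading the same losses leave about 23 and 16 (26 × 0.90 = 23.4; 21 × 0.75 = 15.75). Two-sided power is then about 56% for Mann-Whitney on post scores against 70/86/95% adjusted at rho 0.5/0.7/0.8.
- Data Collection places the baseline tests after randomisation, so adjustment assumes that knowing the allocation does not shift those scores.

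This is a matter of precision and conditional bias, not of false-positive rate. The mismatch between a sample size for two means and a rank test is minor: about 3 points (70% against 67%, two-sided, on post scores).

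**What to change.** In Analysis Statistical:
- Name as the main between-arm analysis, for each score, a mixed model with the post-programme and 3-month scores as outcomes, the baseline score of the same test as covariate, and arm, visit and arm-by-visit as fixed effects. A model that includes baseline as an outcome but constrains the arms to a common baseline mean is an acceptable alternative.
- Report the adjusted mean difference with its 95% confidence interval at each follow-up visit.
- State whether tests are one- or two-sided, since this section is silent and the sample size is one-sided.
- Keep Mann-Whitney on change, or rank ANCOVA where the distribution is doubtful, as sensitivity analyses, and describe Wilcoxon and Friedman as within-arm description.

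The cost is a paragraph of SAP wording and a few lines of R or SPSS, with no new data, visits or patients. It should be fixed before any outcome data are compared by arm.

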## **2. Main objective**

- To evaluate the impact of a therapeutic dance therapy program on cognitive functions, specifically on memory and executive functions, in patients diagnosed with severe mental disorder by measuring scores on neurocognitive tests such as the BACS and MOCA (subsequently defined in the section on data collection) and by analysing electroencephalographic activity.

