## **3. Secondary objectives**

- 1) To compare the scores obtained from the neurocognitive test battery between the experimental group and the control group.
- 2) To compare the changes in brain activity patterns recorded by electroencephalography between the experimental group and the control group.
- 3) To analyze the changes generated in both groups in order to be able to identify the

possible correlations between the improvement in cognitive functions and the alterations in brain activity.

- 4) To evaluate the effects of a 20-session dance therapy program on the symptomatology of people with SMD using the PANSS (later presented in the section on data collection).

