## **STUDY METHODOLOGY**

### **1. Design**

A single-centre prospective randomised controlled trial will be conducted with a minimum of 47 patients with severe mental disorder (SMD) who will be randomly assigned into two groups, 1 intervention group receiving dance therapy (n=26) and 1 control group who will not receive any intervention or added treatment apart from continuing with their usual treatment (pharmacological), but will not receive intervention with dance therapy (n=21).

In summary, the groups are:

- Experimental group (n=26): people with SMD receiving dance therapy.
- Control group (n=21): people with SMD who do not receive the dance therapy intervention but do receive their usual pharmacological treatment.

Tests will be administered before the start of the study and at the end of the study, as well as 3 months after the end of the study in order to compare the results between groups.

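### No score, visit or contrast is designated to test H1a and H1b, every test is run at 0.05 with no multiplicity rule, and no listed test or model term is tied to either hypothesis

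*Combined protocol and SAP*

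**What the plan says.** - **Hypotheses (1. Hypothesis).** H1a reads "People participating in the dance therapy program show significant improvements in memory test scores compared to the control group". H1b says the same of executive functions. The null is non-directional ("there is no significant difference between the neurocognitive test scores and the electroencephalographic activity patterns") while the alternative is directional.
- **Objectives.** The main objective is to be met "by measuring scores on neurocognitive tests such as the BACS and MOCA", together with EEG. The between-arm comparison that H1a and H1b assert is listed under 3. Secondary objectives: "To compare the scores obtained from the neurocognitive test battery between the experimental group and the control group".
- **Candidate scores.** 2. Study variables names domains, not scores. 3. Data Collection lists seven BACS entries, among them List Learning, Verbal Memory and a digit working-memory task. Tower of London is the only one labelled executive. The section also mentions a BACS composite and MoCA, which covers both domains.
- **Visits.** Testing is at baseline, at programme end and "3 months after the end of the study in order to compare the results between groups" (1. Design). Neither later visit is called primary.
- **Analysis (Analysis statistical).** For quantitative variables "the non-parametric Mann-Whitney U, Kruskal-Wallis, Wilcoxon and Friedman tests will be used". A mixed model comes afterwards, with no outcome, terms or contrast, on the ground that "mixed models allow the data to be analyzed, correcting this problem with multiple measurements per individual". The alpha "risk for all hypothesis tests will be 0.05". Sidedness is not stated, and no hierarchy or adjustment appears anywhere.
- **Sizing (e. Sample size calculation).** One-sided, alpha 0.05, 80% power, using PANSS negative symptoms, which belong to the secondary variables.

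**The concern.** The hypotheses use confirmatory language, but several scores, two visits and several tests could each be put forward as the result for H1a or H1b, each at an unadjusted 0.05. A reader of a positive report could not tell a planned result from a selected one.

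Two further points follow from the list of methods. Two of the four rank tests do not compare the arms at all. The one that does in a two-arm trial (Mann-Whitney, to which Kruskal-Wallis reduces with two groups) uses the baseline measurement only if it is run on change scores, which is not stated. So the power of the main comparison depends on a choice the plan leaves open.

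**Working it through.** **1. Which listed method can test H1a or H1b?**

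| Method | What it compares | Can it test a between-arm hypothesis? |
|---|---|---|
| Wilcoxon (listed apart from Mann-Whitney, so the paired test) | two visits within an arm | No |
| Friedman | three visits within an arm | No |
| Mann-Whitney / Kruskal-Wallis | arms | Yes, but post or change scores not stated |
| Mixed model | depends on its terms | Only with an arm contrast, and none is given |

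**2. Sidedness.** The plan's only figure that depends on sidedness is 28 per group. With n = 2[SD(z_alpha + z_beta)/delta]², delta = 2 and one-sided z values 1.645 + 0.842:
- SD 2.822 gives 24.6, so 25; 25/0.90 = 27.8, so 28.
- SD 2.588 gives 20.7, so 21; 21/0.75 = 28.

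The 28s therefore reproduce one-sided, with losses included. Two-sided, the same inputs give 32 and 27, or 36 and 36 after losses. At 26/21 those inputs give 81% power one-sided and 72% two-sided. These are PANSS inputs and say nothing about power for memory or executive scores. They show only that the unstated choice matters.

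**3. False results favouring dance.** Only a result favouring dance supports H1a or H1b, so only that tail is counted. For k scores with common correlation rho and critical value c, P(at least one) = 1 − E[Φ((c − √rho·U)/√(1 − rho))^k], U standard normal. At rho = 0 this is 1 − Φ(c)^k; for example 1 − 0.975³ = 7.3%. The correlations are assumptions.

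| One visit | rho 0 | 0.5 | 0.7 |
|---|---|---|---|
| One named score, two-sided 0.05 | 2.5% | 2.5% | 2.5% |
| H1a, three memory scores, two-sided 0.05 | 7.3% | 6.3% | 5.5% |
| H1a, three memory scores, one-sided 0.05 (nominal 5%) | 14.3% | 11.8% | 10.3% |
| H1a and H1b, one named score each, two-sided | 4.9% | 4.5% | 4.2% |
| H1a and H1b, four scores, two-sided | 9.6% | 7.8% | 6.5% |
| H1a and H1b, five scores, two-sided | 11.9% | 9.1% | 7.4% |

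The five are List Learning, Verbal Memory, the digit task, Tower of London and MoCA. Four applies if the first two overlap or MoCA is not counted. If five scores count at both visits, the figures are about 22% / 14% / 11% with all ten tests equally correlated, or 19% / 14% / 12% with a same-score correlation of 0.7 across visits.

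**4. Power of the between-arm comparison.** Assumptions: normal data, 26/21, true difference d = 0.8 SD, two-sided 0.05, baseline correlation r. The signal is d/√[v(1/26 + 1/21)], with √(1/26 + 1/21) = 0.293. The variance factor v is 1 for post scores, 2(1 − r) for change scores and 1 − r² with baseline adjustment. At r = 0.6 the signals are 2.73, 3.05 and 3.41. Simulated power (20,000 trials per cell):

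| Method | r 0.5 | 0.6 | 0.7 |
|---|---|---|---|
| Mann-Whitney, post scores | 73% | 73% | 73% |
| Mann-Whitney, change scores | 73% | 82% | 91% |
| Baseline-adjusted (ANCOVA) | 86% | 91% | 96% |

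The noncentral t for the corresponding parametric tests at r = 0.6 gives 76%, 85% and 91.5%, which agrees; rank tests lose a little on normal data.

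**The case against.** Much of the intended contrast can be inferred:
- The hypotheses speak of improvement after the intervention, 1. Workplan measures effects after the 20 sessions, and 3. Data Collection calls the 3-month tests a follow-up. Programme end is clearly implied.
- H1a and H1b are directional and the sizing is one-sided.
- H1b has a single labelled BACS score, so the choice of score is mainly an H1a problem.

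All of this stands. It narrows the gap without closing it: 1. Design compares the groups at both visits, MoCA also covers executive function, and nothing on visit or direction is carried into the analysis section.

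The score count may also be too high. The BACS prose names six assessments and the list has seven, so List Learning and Verbal Memory may overlap, and MoCA is given only as a 0 to 30 total. This is why four to five scores are shown.

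The sentence on repeated measurements is not baseless. Averaging two visits correlated 0.5 or 0.7 is worth 47 × 2/(1 + rho) = 63 or 55 patients measured once. But it adds no independent patients, and with complete data a second visit adds essentially nothing to a single-visit contrast. The sentence is misleading rather than simply false.

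Finally, if both hypotheses had to succeed, no alpha split between them would be needed. That is correct, but the plan does not say which rule applies, and the choice of score and visit within each hypothesis would stay open.

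**Conclusion.** The concern holds. The plan states between-arm hypotheses but designates no score, visit or contrast for them, sets no multiplicity rule, and ties none of its methods to them. This should be corrected.

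The size is moderate. For H1a alone, false support for dance rises from 2.5% to about 5.5% to 7% (two-sided tests, one visit). For H1a and H1b together it is about 6.5% to 12%, and higher if both visits count. Leaving baseline adjustment unspecified puts up to about 13 points of power at risk against post scores at r = 0.5 (86% against 73%) and about 23 at r = 0.7 (96% against 73%). Against change scores the loss shrinks from about 13 to 5 points. These sizes rest on assumed correlations, an assumed effect of 0.8 SD, normal data and 26/21 evaluable. The omission itself is textual and does not depend on them.

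A reader might infer more than the documents support:
- **That within-arm change will be reported as benefit.** The tests are listed, but nothing says they will be read that way.
- **That time point and direction are wholly absent.** Both are implied elsewhere.
- **That the relevant error is the chance of any significant result in either direction.** For five scores at one visit that is 23% / 18% / 15%, but results favouring control cannot support H1a or H1b.

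**What to change.** Amend Analysis statistical, dated before outcome data are examined, to:
1. Name one memory score for H1a, the sponsor choosing it and stating which entry in 3. Data Collection it is, and one executive score for H1b (Tower of London is the labelled BACS score). Make end of programme the primary visit.
2. Estimate each as the between-arm difference adjusted for the baseline score, by ANCOVA or by the arm-by-visit contrast of the planned mixed model with small-sample degrees of freedom (Kenward-Roger or Satterthwaite), with its 95% interval. Keep Mann-Whitney on change scores as a sensitivity analysis and make Wilcoxon and Friedman descriptive.
3. State sidedness, consistent with the sizing or with the difference explained.
4. State the success rule: Holm at overall 0.05 if either hypothesis alone can support a claim; no split if both must succeed.
5. Label all other scores, the 3-month visit and the EEG tests secondary or exploratory for inference, and reword the repeated-measurement rationale.

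Align 2. Main objective, 3. Secondary objectives and 2. Study variables so that the between-arm comparison of the named scores is primary. Whether MoCA and EEG stay in the wording of the main objective is for the sponsor to decide.

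**Cost.** A protocol amendment, with no new data; R is already named for the analysis. There will be fewer confirmatory results. If Holm applies, baseline-adjusted power at its 0.025 step (two-sided, 26/21, baseline correlation 0.5 / 0.6 / 0.7) is about 78% / 85% / 92% at d = 0.8, but only 36% / 42% / 52% at d = 0.5.
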